## 10.2 BLOOD SAMPLING TIME SCHEDULE

Visit	Day	Course	Time Point [hh:min]	CRF Time/ planned time	Sample No	Repeated course
2	1	1	-0:05	-0:05	1	
			0:00 Start of infusion	0:00		
			0:15	0:15	2	
			0:30	0:30	3	
			0:45	0:45	4	
			1:00 Immediately prior to end of infusion of BI 6727	1:00	5	CnR1
			1:30	1:30	6	
			2:00	2:00	7	
			4:00	4:00	8	
			8:00	8:00	9	
3	2	1	24:00	24:00	10	CnR2
4	3	1	48:00	48:00	11	
5	5	1	96:00	96:00	12	
6	8	1	168:00	168:00	13	CnR3
7	15	1	336:00	336:00	14	CnR4

Cn = number of course (n ≥ 2)

For repeated courses blood sampling will be performed 1:00 h after start of infusion (immediately prior to end of infusion) and 24:00, 168:00 and 336:00 h after drug administration.

Please note: Blood samples during infusion have to be taken in the opposite arm of the infusion arm.

## 10.4. TUMOUR ASSESSMENT ACCORDING TO RECIST

### 10.4.1 Tumour assessment

#### Measurable disease

Measurable lesions are defined as those that can be accurately measured in at least one dimension (longest diameter to be recorded) as  $\geq 20$  mm with conventional techniques (CT, MRI) or as  $\geq 10$  mm with spiral CT scan. All tumour measurements must be recorded in millimetres (or decimal fractions of centimetres).

Clinical lesions. Clinical lesions will only be considered measurable when they are superficial (e.g., skin nodules and palpable lymph nodes). In the case of skin lesions, documentation by colour photography, including a ruler to estimate the size of the lesion, is recommended.

Conventional CT and MRI. These techniques should be performed with cuts of 10 mm or less in slice thickness contiguously. Spiral CT should be performed using a 5 mm contiguous reconstruction algorithm.

Ultrasound. Ultrasound should not be used to measure tumour lesions. The same holds true for endoscopy or laparoscopy.

#### Non-measurable disease

All other lesions (or sites of disease), including small lesions (longest diameter  $< 20$  mm with conventional techniques or  $< 10$  mm using spiral CT scan), are considered non-measurable disease. Bone lesions, leptomeningeal disease, ascites, pleural/pericardial effusions, lymphangitis cutis/pulmonis, inflammatory breast disease, abdominal masses (not confirmed or followed by CT or MRI), and cystic lesions are all non-measurable.

#### Target lesions

All measurable lesions up to a maximum of five lesions per organ and ten lesions in total, representative of all involved organs, should be identified as target lesions and recorded and measured at baseline. Target lesions should be selected on the basis of their size (lesions with the longest diameter) and their suitability for accurate repeated measurements (either by imaging techniques or clinically). A sum of the longest diameter for all target lesions will be calculated and reported as the baseline sum longest diameter. The baseline sum longest diameter will be used as reference by which to characterize the objective tumour response.

### Non-target lesions

All other lesions (or sites of disease) should be identified as non-target lesions and should also be recorded at baseline. Non-target lesions include measurable lesions that exceed the maximum numbers per organ or total of all involved organs as well as non-measurable lesions. Measurements of these lesions are not required, but the presence or absence of each should be noted throughout follow-up.

#### **10.4.2 Evaluation of target lesions**

Complete Response (CR): disappearance of all target lesions

Partial Response (PR): at least a 30 % decrease in the sum of the longest diameter of target lesions, taking as reference the baseline sum longest diameter

Progressive Disease (PD): at least a 20 % increase in the sum of the longest diameter of target lesions, taking as reference the smallest sum longest diameter recorded since the treatment started or the appearance of one or more new lesions

Stable Disease (SD): neither sufficient shrinkage to qualify for PR nor sufficient increase to qualify for PD, taking as reference the smallest sum longest diameter since the treatment started

#### **10.4.3 Evaluation of non-target lesions**

Complete Response (CR): disappearance of all non-target lesions

Incomplete Response/ Stable Disease (SD): persistence of one or more non-target lesion(s)

Progressive Disease (PD): appearance of one or more new lesions and / or unequivocal progression of existing non-target lesions

#### **10.4.4 Evaluation of best overall response**

The best overall response is the best response recorded from the start of the treatment until disease progression / recurrence (taking as reference for progressive disease the smallest measurements recorded since the treatment started). The patient's best response assignment will depend on the achievement of both measurement (overall response, Table 10.4.4: 1).

The overall responses for all combination of tumour response (target and non-target lesions) with and without appearance of new lesion is given in Table 10.4.4: 1

Table 10.4.4: 1 Overall responses for target and non-target lesions with and without appearance of new lesion

Target lesions	non-target lesions	new lesions	overall response
CR	CR	no	CR
CR	incomplete response / SD	no	PR
PR	non-PD	no	PR
SD	non-PD	no	SD
PD	any	yes or no	PD
any	PD	yes or no	PD
any	any	yes	PD

The examinations should be performed at screening and in line with RECIST after every second course of treatment if the patient qualifies for further courses. Tumour measurements at earlier time points after start of study treatment may be performed if clinically indicated as assessed by the investigator. Tumour measurements during the follow-up period after discontinuation of the study treatment are optional. Imaging results can be used at screening if they were done within the previous four weeks, i.e. no repeat investigation is requested for the purpose of the study.

To be assigned a status of CR, PR, or SD, changes in tumour measurements should be confirmed by repeat assessments that should be performed according to RECIST.

In the case that an assessment of the target and non-target lesion of a patient could not be made by the investigator the category "non-evaluable" (NEV) should be used. In case of absence of non-target lesion at baseline the category of NEV has to be used. The overall responses for all combination of tumour response (target and non-target lesions) with and without appearance of new lesion and non-evaluable lesion measurements is given in Table 10.4.4: 2

Table 10.4.4: 2 Overall responses for target and non-target lesions with and without appearance of new lesion and non-evaluable lesion measurements

Target lesions	non-target lesions	new lesions	overall response
NEV	Any, except of PD	no	NEV
NEV	PD	yes or no	PD
Any, except of PD	NEV	no	response criteria of target lesion
PD	NEV	yes or no	PD
any	any	yes	PD

If the overall response is NEV the additional categories (NEVCNP and NEVCNP) will be used. Description see Table 10.4.4: 3. In the case that a tumour measurement was not performed please see handling of missing value (section 10.4.5).

Table 10.4.4: 3 Tumour response criteria in the case of no assessment of the tumour by the investigator

Label of tumour response	Shortcut	Tumour Response
Non-evaluuable, clinically not progressive	NEVCNP	No assessment of the tumour is possible, but the investigator rated the patient's disease status as clinically not progressive
Non-evaluuable, clinically progressive	NEVCP	No assessment of the tumour is possible, but the investigator rated the patient's disease status as clinically progressive

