#### 10.4.5 Handling of missing tumour lesion measurements

One to ten target lesions (not exceeding 5 lesions per organ) should be identified at screening. These lesions should be followed up with the same method(s) used at screening and their size will be recorded in millimetres.

If target lesions selected at baseline become non-evaluable (i.e. different technique used or missing of tumour lesion measurement, etc), the following rules will be applied

- Analysing strategies:

missing imaging at one time point: if there are lesion measurements during the next course then the non-evaluable tumour evaluation will be reassessed as follows - in case of objective response and stable disease the previous tumour evaluation will be assessed as non-evaluable but no progressive disease (NEVNPD censored with reassessment REASS), the time point of the following non-evaluable measurement will be used for tumour response duration. In the case of progressive disease the previously non-evaluable measurement will be reassigned with non-evaluable but progressive disease (NEVPD censored with reassessment REASS).

- one of the tumour lesions was missed but tumour imaging will be performed within one week of the scheduled time point - this new imaging will be used
- for determination of time of tumour response - the latest time point will be used except in the case of progressive disease when the earliest time point will be used.

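### NEV covers both non-target lesions absent at baseline and those not assessed, so Table 10.4.4: 2 can give an overall CR that has not been shown

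*Protocol*

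**What the plan says.** Protocol section 10.4.4 introduces NEV in two consecutive sentences. The first begins "In the case that an assessment of the target and non-target lesion of a patient could not be made by the investigator the category" and goes on to name NEV. The second reads "In case of absence of non-target lesion at baseline the category of NEV has to be used". The code therefore has two sources: lesions not assessed, and non-target lesions that never existed.

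Table 10.4.4: 2 has one row for non-target NEV when the target is anything but PD and there is no new lesion. The overall response in that row is the "response criteria of target lesion".

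Table 10.4.4: 1 covers assessed lesions. Target CR with non-target "incomplete response / SD" gives PR, and non-target PD gives PD whatever the target response. Section 10.4.3 defines non-target CR as "disappearance of all non-target lesions". Under the non-target lesions heading of section 10.4.1, measurement is not required, but "the presence or absence of each should be noted throughout follow-up".

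SAP section 5.2.1 analyses the overall response entered in the eCRF. It says that a modified RECIST will be used to deal with NEV, through an algorithm that distinguishes target from non-target NEV, with a clinical assessment as the fallback. The details are redacted.

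**The concern.** The two sources of NEV call for different handling. If there was no non-target disease at baseline, the target response is the whole answer and carrying it over is correct. If there was non-target disease that nobody looked at, carrying the target response over treats missing information as if the disease had gone. A patient with target CR and persisting non-target lesions then gets a better category unassessed than assessed. This also departs from the protocol's own requirement in section 10.4.3 that non-target lesions be shown to have disappeared.

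What is at stake is the reported number of complete responses, the split between CR and PR, and each affected patient's best overall response. If the unassessed lesions had progressed, a progression goes unrecorded.

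**Working it through.** No sample size or probability enters this point, and the plan states no figure to reproduce. The check applies Tables 10.4.4: 1 and 10.4.4: 2 as a decision rule.

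Inputs: target response CR, PR or SD; no new lesion; true non-target status absent at baseline, disappeared, persisting or progressing. For lesions present at baseline, each combination is scored twice: once assessed (Table 10.4.4: 1) and once not assessed, hence NEV (Table 10.4.4: 2).

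| Target | True non-target status | Overall if assessed | Overall if non-target is NEV |
|---|---|---|---|
| CR | absent at baseline | (always NEV) | CR, as intended |
| CR | disappeared | CR | CR |
| CR | persisting | PR | **CR** |
| CR | progressing | PD | **CR** |
| PR | absent at baseline | (always NEV) | PR, as intended |
| PR | disappeared | PR | PR |
| PR | persisting | PR | PR |
| PR | progressing | PD | **PR** |
| SD | absent at baseline | (always NEV) | SD, as intended |
| SD | disappeared | SD | SD |
| SD | persisting | SD | SD |
| SD | progressing | PD | **SD** |

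With non-target lesions present at baseline there are 3 target responses × 3 true statuses = 9 combinations. The score depends on whether the lesions were assessed in 4 of them, and 5 are unchanged. These are counts of rule outcomes, not of patients.

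Effect on objective response (CR or PR):
- Target CR, lesions persisting: PR becomes CR. The patient is a responder either way, so the count is unchanged.
- Target CR or PR, lesions progressing: PD becomes CR or PR. The count rises by one for each such patient.
- Target SD, lesions progressing: PD becomes SD. The count is unchanged.

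Fully missed scan: the target is then NEV as well, and the first row of Table 10.4.4: 2 gives overall NEV. No CR results.

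Next, does any other visible rule separate the two meanings?
- Section 10.4.5 opens its rules with "If target lesions selected at baseline become non-evaluable", so they are written for target lesions. The allowance for re-imaging within one week may rescue some assessments, but it does not split the code.
- The clinical sub-categories in Table 10.4.4: 3 apply only when the overall response is NEV. Here it is CR, PR or SD, so they are not reached.
- Confirmation is required ("changes in tumour measurements should be confirmed by repeat assessments that should be performed according to RECIST"), but nothing there says that the non-target lesions must be evaluable. In SAP section 5.2.1 the confirmed endpoint pools CR and PR, so it does not verify a CR. Unconfirmed Best Overall Response takes the best single assessment before PD, so one such CR would set it.
- The visible part of the SAP algorithm depends on which lesion type is NEV, not on why it is NEV.

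**The case against.** The strongest reply is that the rule that matters may be the one that cannot be seen. The SAP says that it modifies RECIST specifically for NEV measurements and treats target and non-target NEV differently, and the details are blacked out. They may already separate the two cases, and redaction is no fault in the plan. The analysis also starts from the investigator's eCRF answer, so an overall CR would need an investigator to report it despite known, unassessed disease. This stands as a limit: the documents do not show that any wrong CR reaches the analysis. It does not rescue the protocol table, which gives that category on its face and should agree with whatever the SAP does.

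A second reply reads the first NEV sentence as covering only patients in whom target and non-target lesions were both unassessable. Absence at baseline would then be the only source of non-target NEV alone, and the row would be right. But Table 10.4.4: 2 has separate rows for target NEV and for non-target NEV, which does not fit that reading, and the text does not state the restriction.

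Three stronger inferences are tempting, and the documents do not support them:
- A reader might infer that every such patient is a false CR. The unassessed lesions may have disappeared, and the CR is then true though not demonstrated.
- A reader might infer that missed scans in general inflate the CR count. A fully missed scan gives overall NEV, so only unassessed non-target lesions alongside evaluable target lesions matter.
- A reader might size the effect as one patient out of a tier of three to six. That presumes an affected patient in the smallest tiers, and no frequency is given. Measurable disease is mandatory only for the 18 additional patients at the MTD (section 3.3.1), and patients without a measurable lesion are NEV overall anyway (section 7.3.2).

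**Conclusion.** Wrong as written, with a small effect. One code has two meanings, and the single table row fits only one of them. Where target lesions are in CR and baseline non-target lesions alone were not assessed, the protocol assigns an overall CR that has not been shown. Where unassessed non-target lesions progressed, the same row records CR, PR or SD in place of PD.

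The consequence is confined to the CR/PR split and best overall response, which are secondary endpoints analysed descriptively (Protocol sections 2.3 and 7.2). The objective response count moves only when the target is CR or PR and the unassessed lesions had progressed. The MTD is unaffected. The number of patients cannot be estimated, because the documents say nothing on how often non-target lesions go unassessed. The conclusion rests on reading Table 10.4.4: 2 as it stands, and on no visible text overriding it. The redacted SAP algorithm could remove the effect from the analysis, though not the ambiguity from the protocol.

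**What to change.** In section 10.4.4, add a separate code for no non-target lesion at baseline and keep the existing Table 10.4.4: 2 outcome (overall response equals target response) for that code only.

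For baseline non-target lesions present but not assessed, state that target CR cannot be scored overall CR. Score PR as the conservative category until the lesions are assessed. This is a convention: Table 10.4.4: 1 has no row for unassessed lesions, and PR would still count a patient with hidden progression as a responder. For the same reason, flag target PR or SD with unassessed non-target lesions in the response listing, so that those results can be read with the gap in view.

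Align the table with the SAP's NEV algorithm, or confirm that the algorithm already makes the distinction.

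Cost: one extra eCRF or derivation code, one more table row, a sentence or two in section 10.4.4 and a flag in a listing. No additional assessments or patients are needed.

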#### 10.4.5 Handling of missing tumour lesion measurements

One to ten target lesions (not exceeding 5 lesions per organ) should be identified at screening. These lesions should be followed up with the same method(s) used at screening and their size will be recorded in millimetres.

If target lesions selected at baseline become non-evaluable (i.e. different technique used or missing of tumour lesion measurement, etc), the following rules will be applied

- Analysing strategies:

missing imaging at one time point: if there are lesion measurements during the next course then the non-evaluable tumour evaluation will be reassessed as follows - in case of objective response and stable disease the previous tumour evaluation will be assessed as non-evaluable but no progressive disease (NEVNPD censored with reassessment REASS), the time point of the following non-evaluable measurement will be used for tumour response duration. In the case of progressive disease the previously non-evaluable measurement will be reassigned with non-evaluable but progressive disease (NEVPD censored with reassessment REASS).

- one of the tumour lesions was missed but tumour imaging will be performed within one week of the scheduled time point - this new imaging will be used
- for determination of time of tumour response - the latest time point will be used except in the case of progressive disease when the earliest time point will be used.

2. LIST OF ABBREVIATIONS

Term	Definition / description
ADS	Analysis Data Set
AE	Adverse event
ALT	Alanine aminotransferase
AST	Aspartate aminotransferase
ALKP	Alkaline phosphatase
BI	Boehringer Ingelheim
BMI	Body mass index
bpm	Beats per minute
[REDACTED]	[REDACTED]
[REDACTED]	[REDACTED]
°C	Degree centigrade
CPK	Creatinine phosphokinase
CR	Complete response
CT	Concomitant therapies
CTR	Clinical trial report
CTCAE	Common terminology criteria for adverse events Version 3.0
CTP	Clinical trial protocol
DLT	Dose limiting toxicity
DQRM	Data quality review meeting
eCRF	Electronic case report form
ECG	Electrocardiogram
ECOG	Eastern Cooperative Oncology Group
GGT	γ-Glutamyl transpeptidase

Term	Definition / description
HR	Heart rate [bpm]
ICH	International Conference on Harmonization
INR	International normalized ratio of prothrombin time
max	Maximum
MedDRA	Medical dictionary for drug regulatory activities
min	Minimum
MTD	Maximum tolerated dose
N	Number of non missing observations
n. a.	Not applicable
NEV	Non-evaluable
NEVCNPD	Non-evaluable but clinically not progressive disease
NEVCPD	Non-evaluable but clinically progressive disease
O*C	Oracle clinical database
PD	Progressive disease
PFS	Progression free survival
PK	Pharmacokinetic
PR	Partial response
PT	Preferred term
PTT	Partial thromboplastin time
PV	Protocol violation
QTcF	QT interval, corrected according to Fridericias formula [ms]
RECIST	Response evaluation criteria in solid tumours
REML	Restricted maximum likelihood

Term	Definition / description
██████████	██████████
SAE	Serious adverse event
SD	Stable disease
SD	Standard deviation
SOC	System organ class
SOP	Standard operating procedure
██████████	██████████
WBC	White blood cell count

3. INTRODUCTION

This Trial Statistical Analysis Plan (TSAP) provides further details on the statistical analyses described in the Clinical Trial Protocol (CTP) dated 3rd October 2005, and subsequent amendments (3) up to 26th June 2008.

3.1 CLINICAL OBJECTIVES

The primary objective of this trial is to determine the Maximum Tolerated Dose (MTD) of BI 6727 therapy in terms of drug-related adverse events.

Secondary objectives are the collection of overall safety and anti-tumour efficacy data and the determination of the pharmacokinetic profile of BI 6727.

3.2 STATISTICAL DESIGN / MODEL

This phase I trial was performed according to an uncontrolled, open label, accelerated dose titration design to determine the MTD of BI 6727 in patients with advanced solid tumours.

The design is that of a 3+3 fixed dose escalation design ([R01-0028](#)) using a toxicity guided approach.

Patients with advanced solid tumours were eligible for this trial. BI 6727 was given as a short infusion over 60 minutes on day 1 of each three week treatment course during the escalation phase. The additional patients treated at the phase II recommended dose of 300 mg to investigate QTc changes, were assigned to one of two infusion time schedules: BI 6727-1h-infusion in course 1 and BI 6727-2h-infusion in course 2 or BI 6727-2h-infusion in course 1 and BI 6727-1h-infusion in course 2. The infusion schedule in courses 3 and higher was always the one hour infusion time.

Patients were not randomized, instead they were selected by the investigators and assigned to the cohort being filled at the time the patient was ready to enter the trial. Thus, the analyses will focus on the exploratory description of the results of each cohort, rather than comparing cohorts.

3.3 NULL AND ALTERNATIVE HYPOTHESES

All analyses in this trial are descriptive and exploratory by nature. Any statistical tests are performed only to provide a statistical framework from which to view the results and plan further studies. No formal statistical inferences are foreseen.

3.4 STATISTICAL SOFTWARE

A trial database within the Oracle Clinical™ (O*C) database system was used to store the study data.

The evaluation of the clinical and the PK data and the statistical analyses will be performed within the validated working environment CARE (Clinical data Analysis and Reporting Environment), including SAS® (current version 8.2, by [REDACTED]
[REDACTED]
[REDACTED]

The calculation of the pharmacokinetic parameters will be performed with WinNonlin® (Professional Network version 5.0.1, [REDACTED]
[REDACTED]

4. CHANGES IN THE PLANNED ANALYSIS OF THE STUDY

Some newly created endpoints regarding tumour response are created and explained within the TSAP.

Following Amendment 3, a more extensive analysis of electrocardiograms (ECG) is planned on the additional cohort of 14 patients. The main aim of this cohort was to investigate QTc changes in parallel with PK sampling during and after intravenous infusion of BI 6727 300 mg dose over 1 hour and over 2 hours. For this set of 12 patients a different analysis of ECG data is planned (see [Section 7.7.4.1](#)).

